### **3.6 Safety Analyses**

Safety will be assessed by summarizing the incidence and type of AEs and SAEs. Laboratory parameters will be provided in the data listings.

Days of exposure, number of doses and total amount of drug received for each subject will be summarized by cohort and overall.

Time on study will be categorized into intervals and summarized by cohort and overall.

The time on study will be defined as the total number of days a subject is known to be followed on study calculated as follows:

$$\text{Time on study} = \text{Last date on study} - \text{Date of first dose} + 1.$$

Where the last date on study is defined as the date of the latest visit or evaluation or telephone contact, or time of death from all available data for a given subject.

#### **3.6.1 Adverse Events**

The incidence of AEs will be summarized by Medical Dictionary for Regulatory Activities (MedDRA) preferred term and system organ class for:

- Any treatment emergent adverse events
- Related treatment emergent adverse events. Related adverse event is defined as those events with related or possible related relationship to study drug.
- Any treatment emergent adverse events by severity
- Related treatment emergent adverse events by severity
- Serious treatment emergent adverse events
- Serious and related treatment emergent adverse events.
- Lumber puncture related treatment emergent adverse events. Lumber puncture related adverse event is defined as those events with related or possible related relationship to study procedure/other study drug.

AEs that lead to treatment discontinuation will be listed separately. Early dosing termination and early study termination will be summarized by termination reason.

A treatment emergent adverse event is defined as an event occurring after the initiation of study treatment and before the end of the follow-up period. Non-treatment emergent adverse event will be flagged in the data listing.

If there is no “Formlink” link, and the AE (start date/time) occurs after the subject’s first dosing date/time, then the AE is treatment-emergent. Otherwise, if the AE (start date/time) occurs prior to the subject’s first dosing date/time, then the AE is not treatment-emergent.

If there is a “Formlink” link between two AE records, then we compare them pairwise, and consider two cases, where we compare the AE severity (mild/moderate/severe) between the two records in the pair. We chronologically order the 2 records (by AE start date) and refer to the “first” and “second” AEs.

Case 1: The first AE record in the pair occurs before first dosing, and the second record occurs after dosing.

If the AE severity on the second record is worse than the severity on the first record, then only count the second AE as treatment-emergent. But, if the severity improves (second record severity is less severe than the first record severity), then neither record is counted as treatment-emergent.

Case 2: Both AE records in the pair occur after first dosing.

If the AE severity on the second record is worse than the severity on the first record, then count both records as treatment-emergent. But, if the severity improves, then only count the first record as treatment-emergent.

When counting the total number of treatment-emergent events, events linked together through change in severity will still be counted as separate events.

The most conservative approach will be used to determine if the event occurs during the treatment or follow-up periods. For example,

- AEs that have onset dates or resolution dates prior to the first study treatment dates will be considered to have occurred prior to the study period. If the onset or resolution date of an AE is a partial date with only month or year available or completely missing, then the event is assumed to be within the study period unless the year is prior to the year of the first study treatment date, or if in the same year, the month is prior to the month of the first study treatment date.
- AEs that have onset dates after study termination date will be assumed to have occurred after the study period. If the onset of an AE is a partial date with only month or year available or complete missing, then similar approach as above will be used.

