#### **9.4.3.5 Outcome of the Adverse Event**

If the event is a non-serious AE then the event's outcome is characterized by one of the following:

- **AE Persists:** Subject terminates from the trial and the AE continues
- **Recovered:** Subject recovered completely from the AE
- **Became Serious:** The event became serious (the date that the event became serious should be recorded as the Resolution Date of that AE and the Onset Date of the corresponding SAE)
- **Change in Severity (if applicable):** AE severity changed

If the event is a SAE then the event's outcome is characterized by one of the following:

- **Ongoing:** SAE continuing
- **Persists (as non-serious AE):** Subject has not fully recovered but the event no longer meets serious criteria and should be captured as an AE on the non-serious AE electronic case report form (eCRF) (the SAE resolution date should be entered as the date of onset of that AE)
- **Recovered:** Subject recovered completely from the SAE (the date of recovery should be entered as the SAE resolution date)
- **Fatal:** Subject died (the date of death should be entered as the SAE resolution date)

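### The linked-AE rule ignores seriousness: if linked, a post-dose SAE with a lower severity grade leaves the serious treatment-emergent tables, and equal grade has no rule

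*SAP*

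**What the plan says.** SAP 3.6.1 first defines a treatment-emergent event by timing only: it starts after study treatment begins and before follow-up ends. An AE record without a Formlink is classified by its own start date. Two records joined by a Formlink are handled as a pair, "where we compare the AE severity (mild/moderate/severe) between the two records in the pair".

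- Case 1, first record before first dose and second after: a worse second record is the only one of the two that counts. For a milder second record the SAP removes the pair: "if the severity improves (second record severity is less severe than the first record severity), then neither record is counted as treatment-emergent".
- Case 2, both records after first dose: a worse second record means that the two are both counted. For a milder second record the SAP reads: "But, if the severity improves, then only count the first record as treatment-emergent".

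For event totals, "events linked together through change in severity will still be counted as separate events". The planned tables in the same section include serious treatment-emergent events and those that are both serious and related.

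Protocol 9.4.3.5 splits an AE that becomes serious: the date of that change "should be recorded as the Resolution Date of that AE and the Onset Date of the corresponding SAE". It lists becoming serious and changing in severity as separate outcomes. Protocol 9.4.3.2 asks for seriousness criteria in addition to the severity grade.

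**The concern.** Severity and seriousness are different attributes. An event can become serious, for instance through hospital admission (Protocol 9.3.3), with no rise in grade. The pair rule has a sensible purpose, which is not to count an improving event as a new one. It was written for records that differ in grade, however, and it does not ask whether the second record is newly serious.

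If an AE and the SAE it became are linked, the rule can remove a genuine post-dose SAE from the table meant to show it, or leave its status to the programmer. Safety is a secondary objective, and Protocol 10.2 gives adequate safety assessment as the reason for the sample size. In a trial this small, one infant moves the serious incidence visibly.

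**Working it through.** The plan states no figure for this rule, so there is none to reproduce. The check applies the rule as written to every combination.

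**Inputs.** There are three severity grades (Protocol 9.4.3.2; SAP 3.6.1). The first record is a non-serious AE, and the second is the SAE it became, starting after first dose (Protocol 9.4.3.5). The two records are assumed to be linked. The grade pairs number 3 × 3 = 9.

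| SAE grade relative to AE grade | Pairs | Case 1: records counted | Case 2: records counted | SAE in serious table? |
|---|---|---|---|---|
| Higher | 3 of 9 | second only (1) | both (2) | yes |
| Lower | 3 of 9 | neither (0) | first only (1) | no |
| Equal | 3 of 9 | no branch | no branch | undefined |

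These are counts of logical combinations, not expected frequencies.

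**Lower grade.** Take a severe post-dose AE that becomes a moderate SAE. By timing, the SAE is treatment-emergent under the SAP's general definition. Under Case 2 it is not, and only the non-serious record remains. In Case 1 both records go, so the event also leaves the table of all treatment-emergent events. Case 1 can occur, because AEs are collected from consent (Protocol 9.4.2) and screening may begin up to 21 days before first dose (Protocol 3.4.1).

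**Equal grade.** Equal is neither worse nor improved, so neither branch is triggered. The start-date rule for unlinked records does not apply to a linked pair. The general definition would keep the SAE, but the pair rule is what a programmer would code, and it is silent.

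**Unlinked records.** The SAE is classified by its own start date and stays treatment-emergent. Nothing is lost.

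**Size.** One infant changes the incidence by 1/n. At n = 20, 1/20 = 5 percentage points. At n = 8, the lower end of planned enrolment (Protocol 3.3), 1/8 = 12.5 points. This applies only to an infant with no other treatment-emergent SAE. In a system organ class or preferred-term row, it applies to an infant with no other such SAE in that row.

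**The case against.** The strongest objection is that the loss depends on a link the documents never describe. The SAP's remark on event totals speaks of records linked through a change in severity, and the protocol codes becoming serious as a different outcome. A natural reading is that Formlinks mark severity changes only, and then conversions are unlinked and safe. This stands as a condition on the point. It does not dispose of it, because the pair rule covers any link between two AE records and defines none.

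Second, the loss the rule prescribes is confined to an event that becomes serious while its grade falls, which may be uncommon. That also stands. A reader might infer that SAEs of the same grade are dropped too. The text does not say so; at equal grade the defect is a missing branch.

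Third, there are safeguards. Events that are not treatment-emergent are flagged in the listing (SAP 3.6.1), Protocol 10.5.3 plans tables and/or narratives of serious events, and SAE reporting within 24 hours (Protocol 9.4.1) is unaffected. In Case 2 the first record stays in the table of all treatment-emergent events. These limit the harm but do not correct the summary tables.

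Two stronger readings are not supported:

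- **Inflated respiratory SAE rates.** SAP 3.4.1 works from SAEs without applying the treatment-emergent rule. A conversion adds one SAE record, and the protocol lists a change in severity as an outcome only for non-serious AEs.
- **Double counting of worsening events as an error.** The SAP discloses this choice. It arises only in Case 2 and affects event totals. Subject incidence within a period is unchanged, though an infant may appear in more than one 90-day interval (SAP 3.6.1.1).

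**Conclusion.** The point holds in a limited form. If AE-to-SAE conversions are linked, SAP 3.6.1 as written excludes a post-dose SAE of lower grade than the preceding AE from the serious and serious-and-related tables, against the SAP's own timing definition. For an SAE of equal grade it gives no answer.

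The size is 5 percentage points of serious treatment-emergent incidence per affected infant at n = 20, provided that infant has no other treatment-emergent SAE. The documents give neither the number of conversions nor whether they are linked, so no overall effect can be estimated. When the rule drops a record, the effect on the serious tables can only be downward. Nothing here shows that any SAE would go unreported or that the respiratory rates are wrong.

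**What to change.** Amend the pair rule in SAP 3.6.1, in both cases:

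1. The second record is treatment-emergent if it starts after first dose and either its severity is worse or it is newly serious, whatever its grade.
2. If severity is equal and the second record is not newly serious, it is not a new treatment-emergent event and the first record keeps its status. This also covers an SAE that continues at the same grade as a non-serious AE.
3. State that AE-to-SAE conversions fall under this rule if they are linked.

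With this change the SAE is kept in all 9 grade pairs. The existing result for a lower grade stays as it is when the second record is not newly serious.

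The cost is a few lines of SAP text and derivation code. Serious treatment-emergent counts may rise slightly. Because linked records are counted separately, each rescued lower-grade conversion also adds one record to the event total (Case 1 from 0 to 1, Case 2 from 1 to 2). As an option, the number of distinct events can be reported beside the record count.

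### SAP 3.6.1 classifies linked adverse-event records only in pairs, so a sequence of three or more can give one record opposite treatment-emergent flags

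*SAP*

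**What the plan says.** SAP 3.6.1 treats records joined by a Formlink separately from unlinked ones. For linked records, "then we compare them pairwise, and consider two cases". The two records are put in order of start date, and "we compare the AE severity (mild/moderate/severe) between the two records in the pair".

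- **Case 1.** "The first AE record in the pair occurs before first dosing, and the second record occurs after dosing". If the second is worse, only the second counts as treatment-emergent. If it is milder, "then neither record is counted as treatment-emergent".
- **Case 2.** Both records follow the first dose. If the second is worse, both count. "But, if the severity improves, then only count the first record as treatment-emergent".

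The section then adds that records linked by a severity change still count as separate events.

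Linked records arise because Protocol 9.4.3.5 includes a change in severity ("AE severity changed") among the outcomes of a non-serious event. Nothing there limits an event to one change. Recording starts at consent (Protocol 9.4.1 and 9.4.2). Conditions present before consent go to medical history unless they worsen (Protocol 9.4). The SAP's list of modifications describes the linked-record text as a clarification added in this version, so it is meant to be programmed.

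**The concern.** An event that changes grade twice has three records. If they are linked in sequence, the middle record belongs to two pairs, and the SAP does not say which pair decides. Two programmers who both follow the text could flag the same record differently.

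There is a second difficulty. Case 1 counts an event that began before dosing only when it worsens from its pre-dose grade. Once two records lie after dosing, Case 2 compares them with each other and no longer looks at that grade.

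The flag feeds every treatment-emergent table in SAP 3.6.1 and the tables in 3.6.1.1 and 3.6.1.2. Safety is a secondary objective, and SAP 3.1.4 plans interim safety analyses that will supply regulatory submissions.

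**Working it through.** The plan gives no figure to reproduce. The check applies the two cases literally to every possible three-record sequence.

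**Inputs.** Three grades, two at a time, Cases 1 and 2 (SAP 3.6.1). **Assumption:** each record is linked to the next, and each link is a change of grade. **Patterns:** 3 × 2 × 2 = 12.

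**One record before dosing (A), two after (B, C).** Pair A–B falls under Case 1 and pair B–C under Case 2.

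| A–B–C | B by pair A–B | B by pair B–C | C | Ever above A? |
|---|---|---|---|---|
| mild–moderate–mild | count | count | no | yes |
| mild–moderate–severe | count | count | count | yes |
| mild–severe–mild | count | count | no | yes |
| mild–severe–moderate | count | count | no | yes |
| moderate–mild–moderate | **no** | **count** | count | no |
| moderate–mild–severe | **no** | **count** | count | yes |
| moderate–severe–mild | count | count | no | yes |
| moderate–severe–moderate | count | count | no | yes |
| severe–mild–moderate | **no** | **count** | count | no |
| severe–mild–severe | **no** | **count** | count | no |
| severe–moderate–mild | **no** | **count** | no | no |
| severe–moderate–severe | **no** | **count** | count | no |

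Case 2 counts the first record of its pair whether the second is better or worse, so pair B–C always counts B. Pair A–B excludes B exactly when B is milder than A. Three ordered pairs of grades meet that condition, each with two possible values of C: 3 × 2 = 6 conflicts in 12.

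In five patterns the event never exceeds its pre-dose grade. In four of these C is worse than B, so Case 2 counts C, and C is in no other pair. The fifth, severe–moderate–mild, is undetermined: Case 1 says not to count B and Case 2 says to count it.

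**All three records after dosing.** Both pairs fall under Case 2. Pair A–B excludes B when B is milder than A, and pair B–C counts B regardless. Again 6 of 12 conflict. A is counted in all 12.

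**Two before dosing, one after.** No conflicts (0 of 12), though no case covers the pair that lies wholly before dosing.

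**Other link structures.** If A and C are compared as well, conflicts rise to 7 of 12, both for one pre-dose and two post-dose records and for three post-dose records. If every later record is linked only to the opening record, each later record sits in one pair and conflicts fall to 0 of 12 in both settings. A return to the opening grade would then be undefined, because neither case covers equal severity.

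**Reach into the tables.** One infant is 1/20 = 5 percentage points if about 20 are treated, and 1/4 = 25 points in Cohort 1. That is the most one infant can move one term.

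**The case against.** **The link structure is assumed.** The SAP does not say that records are linked in sequence, and linking to the opening record removes the conflicts. This stands as a condition on the result. Sequential linking is plausible, because Protocol 9.4.3.5 records the change as the outcome of the record that is closing, but it is not stated.

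**The conservative-approach sentence could settle it.** A reader could let any positive flag win, since SAP 3.6.1 promises the most conservative approach. That sentence governs whether an event falls in the treatment or follow-up period, and its examples are about dates. It does not settle conflicting severity flags.

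**The pattern needs unusual data.** A reader might infer that the respiratory and feeding problems infants bring into the study would be reported as treatment-emergent. The documents do not support that: conditions present before consent go to medical history unless they worsen. A pre-dose record has to arise between consent and first dose, with screening no more than 21 days before dosing (Protocol 3.4.1), and then change grade twice afterwards. Four of the five patterns that never exceed the pre-dose grade also need a severe pre-dose event, which the exclusion criteria make less likely. Severity change is listed only for non-serious events, so the serious-event tables are little exposed. All of this stands and limits the size.

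**Counting a relapse is defensible.** Severe–mild–severe contains a real worsening after dosing, and a cautious safety table might include it. That is a fair choice, but it is not the principle in Case 1. If the sponsor prefers it, the SAP should say so.

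**Conclusion.** The rule is incomplete and, for records linked in sequence, contradicts itself. A middle record milder than its predecessor gets opposite flags in 6 of 12 patterns, whether the sequence starts before dosing or lies wholly after it. In four patterns that start before dosing, a post-dose record is counted although the event never exceeded its pre-dose grade.

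Two stronger readings do not hold. A reader might infer that a pre-dose event that only improves is counted as treatment-emergent. Severe–moderate–mild is the only such three-record pattern, and its result is undetermined. A reader might also take 6 of 12 as an error rate. It counts patterns, and the documents do not say how often such sequences occur.

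The effect on the tables is limited:

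- **Sequences wholly after dosing.** The first record is always treatment-emergent, so overall subject incidence does not change. Event counts do, and possibly the severity tables. The 90-day tables can also change, because a disputed record starting in a later interval can add the infant to that interval.
- **Sequences starting before dosing.** Subject incidence for a term can change only if the infant has no other treatment-emergent event of that term during about 3.7 years of participation.

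The conclusion rests on sequential linking and on at least one event with three or more records. No effect on any table has been shown. The correction is worth making because it costs little and removes a choice now left to the programmer.

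**What to change.** Replace the pairwise cases in SAP 3.6.1 with a rule that classifies each record once:

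1. **Sequence starting before first dose.** Compare every post-dose record with the worst pre-dose severity in that sequence, and count it only if it is worse. This is the Case 1 principle.
2. **Sequence starting after first dose.** Count the first record. Count each later record only if it is worse than its immediate predecessor. This is the Case 2 principle, and no record is re-flagged by the next pair.

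The SAP should also state how records are linked. The rule settles equal severity (not worse, so not counted) and pairs wholly before dosing (never counted).

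No new data are needed, only a few sentences and minor reprogramming. Some flags change. In the four patterns above, a post-dose relapse to a grade not above the pre-dose grade leaves the tables. The same four grade patterns are affected when two records precede dosing. These records should stay flagged in the listings. In mild–severe–moderate the third record would now be counted, because moderate is worse than the pre-dose grade, so event counts could rise slightly there. Two-record sequences with a change of grade keep their present classification.

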### ***3.6.1.1 Adverse Events over Time***

The incidence of AEs will be evaluated by time of onset by 90-day time intervals. For a given time interval, the number of subjects who were followed for adverse events during that time interval will be presented along with the incidence of adverse events during that time interval. Therefore, for a given System Organ Class (SOC) or preferred term (PT), subjects will be counted only once for a given time interval but may be counted more than once across time intervals.

### ***3.6.1.2 Adverse events following Dosing***

To examine the onset of any adverse events following dosing, the incidence of events that occur during loading and maintenance dosing periods will be presented by treatment group and overall. In addition, presentations of events that occurred in the first 24 hours and the first 72 hours following dosing will be provided.

### ***3.6.2 Laboratory Measurements***

The following is the list of lab analytes that will be collected throughout the study:

- Chemistry: Sodium, Potassium, Chloride, Total protein, Albumin, Calcium, Phosphorus, Bicarbonate, Glucose, BUN, Creatinine, Cystatin C, Total serum bilirubin, ALT, AST, Alkaline phosphatase, CPK
- Hematology: Hematocrit, Hemoglobin, Platelets, RBC, WBC, and WBC differential (Basophils, Eosinophils, Lymphocytes, Monocytes, and Neutrophils)
- Coagulation: PT, aPTT, INR
- Urinalysis: Specific gravity, pH, Protein, Glucose, Ketones, Bilirubin, Blood, Red blood cells, White blood cells, Epithelial cell, Bacteria, Casts, Crystals

- CSF safety: Red blood cells, White blood cells, Glucose, Protein.
- SMN Genetics: SMN2 copy number and SMN gene sequencing

If WBC differential absolute counts are missing, and percentages are available, then the absolute counts will be calculated by multiplying the percentage by total WBC count. Conversely, if absolute counts are available, percentages are missing, percentages will be calculated by dividing absolute count by the total WBC count. If neutrophils counts and percentages are missing, and segmented neutrophils and bands neutrophils results are available, then neutrophils will be calculated by adding segmented neutrophils and bands neutrophils.

Each subject's laboratory values will be classified according to whether the test result is "low" (i.e., below the lower limit of normal [LLN]), "normal" (within the normal range), or "high" (i.e., above the upper limit of normal [ULN]). If a subject is missing a baseline value but had a post-baseline value, then the baseline assessment is labeled as "unknown". Likewise, if a subject had a baseline value but had no post-baseline values, then the minimum and maximum are labeled as "unknown". Post-baseline laboratory results are defined as any assessment taken after the first dose. The shifts (relative to the normal range) from baseline to the minimum and maximum post-baseline values will be presented. Should a treatment affect a laboratory parameter, that parameter could be affected at different times for different subjects. Therefore, these analyses present the most extreme values for each subject. For many laboratory parameters, the effect could be in either direction, (i.e., an increase or a decrease), so both the maximum and minimum values have been analyzed. From these, the shifts (relative to the normal range) from baseline to low and high will be calculated. If a subject's value shifts, it can change from normal to either low or high, from low to normal or high, from high to normal or low, or from unknown to low, normal, or high. For each parameter, the incidence of shift to low will be summarized using the minimum post-baseline values. Shift to low includes subjects with a normal, high, or unknown baseline value and at least one post-baseline value of the given test. Similarly, the incidence of shift to high will be summarized using the maximum post-baseline values. Shift to high includes subjects with a low, normal, or unknown baseline value and at least one post-baseline value.

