## **5.2 Exclusion Criteria**

Subjects meeting any of the following criteria are not eligible for the study:

1. Hypoxemia (O2 saturation awake < 96% or O2 saturation asleep < 96%, without ventilation support)
2. Presence of an untreated or inadequately treated active infection requiring systemic antiviral or antimicrobial therapy at any time during the screening period
3. History of brain or spinal cord disease that would interfere with the LP procedures, CSF circulation, or safety assessments
4. Presence of an implanted shunt for the drainage of CSF or an implanted CNS catheter
5. History of bacterial meningitis
6. Clinically significant abnormalities in hematology or clinical chemistry parameters, as assessed by the Site Investigator, at screening that would render the subject unsuitable for inclusion
7. Treatment with another investigational drug (e.g., albuterol, riluzole, carnitine, creatine, sodium phenylbutyrate, salbutamol, valproate, hydroxyurea, etc.), biological agent, or device within 90 days prior to enrollment or anytime during the study. Any history of gene therapy or cell transplantation
8. The subject's parent(s) or legal guardian(s) is unable to understand the nature, scope, and possible consequences of the study, or does not agree to comply with the protocol defined schedule of assessments
9. Ongoing medical condition that according to the Site Investigator would interfere with the conduct and assessments of the study. Examples are medical disability other than SMA that would interfere with the assessment of safety or would compromise the ability of the subject to undergo study procedures

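### The SAP's laboratory shift tables count new crossings of the normal range, and nothing in the plan gives an incidence of marked worsening, including in infants already abnormal in that direction at baseline

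*SAP*

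**What the plan says.** SAP 3.6.2 sets up three categories: "Each subject's laboratory values will be classified according to whether the test result is" below, within or above the normal range. Baseline is then compared with each infant's minimum and maximum value after the first dose. Two incidences follow:

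- For highs: "Shift to high includes subjects with a low, normal, or unknown baseline value and at least one post-baseline value".
- For lows: "Shift to low includes subjects with a normal, high, or unknown baseline value and at least one post-baseline value of the given test".

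A missing baseline is not a reason for exclusion. The case is introduced with "If a subject is missing a baseline value but had a post-baseline value" and the baseline is labelled unknown. The list of possible shifts ends "or from unknown to low, normal, or high".

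The section has no severity grade, multiple of a limit or size of change. The only other laboratory output named in the SAP's safety section is in 3.6: "Laboratory parameters will be provided in the data listings". Protocol 10.5.3 promises more, namely laboratory and CSF summaries by visit and cohort, and presentation over time against the pre-Day 1 result. SAP 3.6.2 does not specify these.

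The SAP treats ECGs differently. Section 3.6.5 counts infants with a post-baseline QTcF above 450, 480 and 500 msec and infants with increases of 30 and 60 msec, and it states no exclusion for an abnormal baseline.

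**The concern.** Safety is a secondary objective, and the sample size was chosen with safety assessment in mind. The study is open label and not randomised, so an infant's own baseline is the main reference for a laboratory change. The shift incidence uses that baseline only to decide who is eligible and which category applies. It cannot separate a stable mild abnormality from one that has become much worse.

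Such infants can be enrolled. Protocol 5.2 excludes "Clinically significant abnormalities in hematology or clinical chemistry parameters, as assessed by the Site Investigator", and only where these make the infant unsuitable, so milder out-of-range values do not bar entry. The criterion does not mention CSF or urinalysis values.

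At stake is whether a liver, muscle, kidney or CSF signal in an infant who starts mildly out of range would show in a summary table, or would have to be found by reading individual data. A smaller issue runs the other way: an abnormal result with no baseline is counted as a shift although no change has been shown.

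**Working it through.** The plan states no laboratory incidence, so there is no figure to reproduce. The check applies the rule as written and then illustrates its effect.

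**Inputs**
- Categories, eligible baselines and treatment of unknown baselines: SAP 3.6.2.
- Post-baseline value: the infant's maximum for highs and minimum for lows (SAP 3.6.2).
- Baseline: last non-missing value before the first dose (SAP 3.1.1).
- Number of infants: about 8 to 20 (SAP 1.1); 20 is used below.
- I read the sentence on who is included as defining the denominator as well as the numerator.

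**Step 1. The rule for shift to high, case by case**

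| Baseline | Maximum afterwards | Ratio to baseline | In denominator | Counted |
|---|---|---|---|---|
| 1.2 x ULN | 12 x ULN | 12/1.2 = 10 | no | no |
| 0.98 x ULN | 1.02 x ULN | 1.02/0.98 = 1.04 | yes | yes |
| low | high | – | yes | yes |
| unknown | high | – | yes | yes |
| unknown | normal | – | yes | no |

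Shift to low is the mirror image. Only a baseline abnormal in the same direction removes an infant; the third row shows that one abnormal in the other direction stays in.

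**Step 2. Infants high at baseline (all counts assumed)**

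Let N = 20, let x = 2 infants be newly high, let h infants be high at baseline, and let no baseline be missing. The SAP incidence is x/(N − h). If all h infants also worsened markedly, the share newly high or markedly worse would be (x + h)/N.

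| h | SAP shift to high | Newly high, or worse from high, if all h worsen |
|---|---|---|
| 0 | 2/20 = 10.0% | 2/20 = 10% |
| 2 | 2/18 = 11.1% | 4/20 = 20% |
| 5 | 2/15 = 13.3% | 7/20 = 35% |
| 10 | 2/10 = 20.0% | 12/20 = 60% |

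The last column is the upper extreme. If none of the h infants worsened it would be 2/20 in every row. The middle column is the same in both situations, so the shift incidence carries no information about these infants.

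**Step 3. Unknown baselines (all counts assumed)**

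Let h = 0 and x = 2, and let u infants have no baseline and a high value later. The SAP incidence is (x + u)/N. Using known baselines only, it is x/(N − u).

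- u = 1: 3/20 = 15.0% against 2/19 = 10.5%.
- u = 2: 4/20 = 20.0% against 2/18 = 11.1%.

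**The case against.** The strongest reply is that the table does what it sets out to do. An infant already high cannot become newly high, so leaving that infant out of both numerator and denominator is the correct convention for new abnormalities. This stands. A reader might infer that the reported incidence is biased downwards. The documents do not support that: for new abnormalities the exclusion raises the percentage, as 2/18 against 2/20 shows. It looks low only if the event is redefined as any marked worsening.

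A reader might also infer that every infant abnormal at baseline is dropped, or that a large worsening goes unreported. Neither follows. Only same-direction baselines are left out, and other routes exist:

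- **Listings** show the value, but give no incidence.
- **Adverse events.** Protocol 9.3.1, 9.4 and 9.5.1 allow a clinically significant laboratory change, or worsening of a pre-existing condition, to be recorded, and SAP 3.6.1 tabulates events by term and severity. For a laboratory result this depends on the investigator's judgment.
- **By-visit summaries** under Protocol 10.5.3 could show an extreme value as a visit maximum. SAP 3.6.2 does not specify them, and they would not count infants who worsened.
- **Ongoing review** of safety data by the sponsor and the DSMB may pick up a signal, but is not a reported analysis.
- **A full cross-tabulation.** SAP 3.6.2 may intend one as well as the two incidences, since it labels a missing post-baseline extreme unknown. High-to-high and unknown-baseline infants would then have their own cells. A high-to-high cell would still combine stable with tenfold worse.

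The unknown-baseline issue is probably small. Appendix A schedules safety laboratory tests at screening and CSF tests before the Day 1 dose, and SAP 3.1.1 lets unscheduled results supply the baseline. Counting such infants also errs towards over-reporting harm.

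Finally, with 8 to 20 infants the listings can be read one by one. That limits the harm, but it does not replace a prespecified count.

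**Conclusion.** The point holds as a gap in the laboratory safety summary, not as an error in the shift calculation. The incidence tables respond only to crossing a limit. They cannot register worsening in an infant already abnormal in that direction, they give a trivial crossing the same weight as a large one, and they treat an abnormal value with an unknown baseline as a shift. No other planned output supplies an incidence of marked worsening.

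The size is unknown, because the documents give neither the share of infants out of range at entry nor the number of missing baselines. The 2 to 10 infants high at baseline correspond to an assumed 10% to 50% of 20, the top of the planned enrolment. The 1 or 2 missing baselines are likewise assumed. No primary result or decision rule rests on these tables. This is an inexpensive improvement to the reporting of a secondary objective, and the SAP's own QTcF analysis provides the model.

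**What to change.** Keep the shift tables in SAP 3.6.2 and add the following:

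1. For all infants, whatever their baseline category, summarise the worst post-baseline value as a multiple of the upper (or lower) limit and as a ratio to the infant's own baseline, where one exists. Use categories that the sponsor prespecifies, in parallel with the QTcF outlier analysis in SAP 3.6.5.
2. Give infants abnormal in the same direction at baseline their own row, so that worsening among them is visible.
3. Report infants with an unknown baseline separately from the shift incidence.
4. State whether the full baseline-by-extreme cross-tabulation will be produced, and whether the by-visit summaries in Protocol 10.5.3 will be carried out.

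The cost is SAP wording and about one more table per laboratory panel, from data already collected. The downside is more output and a few more flagged values to review. No visit, sample or clinical rule changes.
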